4.4 Withdrawal and discontinuation

Participant are withdrawn from the study if:

- Parent withdraws informed consent.
- Other legal representative (parent) is in disagreement with participation.
- Major protocol deviation occurs in disrespect of inclusion criteria.

Co-investigators are to inform principle and chief investigator of protocol deviation within 24h after they are acknowledged. Withdrawal are to be noted in patient records. Contact details can be kept by co-investigators that follow patients but are to be removed from all other documents (principle and chief investigator list).

4.5 Planned schedule

The Swiss trial is meant to run from February 2021 to at latest September 2021.

	2019												2020												2021											
	1	2	3	4	5	6	7	8	9	10	11	12	1	2	3	4	5	6	7	8	9	10	11	12	1	2	3	4	5	6	7	8	9	10	11	12
Pilot Phase																																				
Osteopath recruitment																																				
Training (dev., training, fidelity)																																				
Pilot data collection																																				
Feasibility evaluation																																				
Global ethical approval																																				
Protocol publication																																				
UK recruitment																																				
Osteopath training for electronic data collection																																				
Data collection																																				
Australian recruitment																																				
Ethical approbation																																				
Osteopath recruitment																																				
Osteopath training																																				
Data collection																																				
Switzerland recruitment																																				
Ethical approbation																																				
Document translation																																				
Osteopath recruitment																																				
Osteopath training																																				
Data collection																																				
Central management																																				
Trial Management																																				
Electronic data collection testing and validation																																				
Quality control																																				
Data cleaning																																				
Data analysis																																				
Report																																				
Publication / congress																																				

5 STATISTICS AND METHODOLOGY

5.1 Statistical analysis plan and sample size calculation

The analysis of the data will be carried out on the entire data collected by the international consortium. The Swiss data is therefore embedded in the overall analysis.

Sample size estimation

The data collected on crying time and standard deviations (SD) during the pilot phase (n=13, one diary was completed incorrectly) was consistent with observations made by (Wolke et al., 2017). We estimated the average daily crying time over the two-week follow-up period to be 120 minutes with a SD of 46 minutes. To detect a minimum of 30 minutes additional reduction in crying time between the intervention and control groups, with 90% power and a two-sided 5% significance

level, we would need 48 infants in each arm of the trial. If we allow for a 15% drop-out rate, we would need to randomise 112 infants or 56 in each arm. Each country is expected to enrol 40 participants or four patients from 10 secondary sites.

Descriptive statistics

Descriptive statistics will be used to summarise the characteristics of participants in each group in the trial. This will include baseline values, treatment schedules, compliance and follow-up. We will show number and percentage or mean and standard deviation for categorical and normally distributed continuous variables respectively. For data severely deviating from a normal distribution, we will present median and interquartile ranges. Probability of observed between groups difference will be calculated by using Fisher's exact, Chi2 test, Mann Whitney U test and, or Student's t-test as appropriate.

For crying time, the Bartlett's periodogram-based test for white noise will be used to test the assumption of constant mean and variance for each individual. Analysis of graphical representation will define which transformation would best model trend over time. If a clear change of effects happens abruptly over time, the data will be additionally analysed over separate time periods, by default separating the first week from the second. If such a trend exists, secondary analysis will also compare differences for indicators of this trend between groups.

Primary outcome analysis

We will analyse the primary outcome of mean crying time using a multilevel mixed-effects generalised linear model (GLM) adjusting for lack of independence at site and at practitioner level. Mean crying time will be entered as the dependent variable and group allocation as the explanatory variable. The hierarchical multilevel datasets are assumed to have normally distributed random effects. Likelihood ratio test will be used to test for clustering effects. Results will be reported as between-group differences in average crying time in hours with 95% confidence intervals. P-values will provide the probability of this difference being null using Wald Chi2 test. If clustering effects cannot be identified ($p\text{-value} > 0.05$), further analysis (i.e. sensitivity analysis, adjusted analysis, etc.) will use simple logistic regression without accounting for lack of independence.

Secondary outcomes analysis

The same method will be used to test secondary outcomes. Categorical response variables using Likert scales (i.e. global change, parent satisfaction) will be analysed using a proportional odds model. Between group changes in parenting confidence score will compare changes from baseline by entering baseline score as an explanatory variable in the GLM model.

Proportion of participants who reported at least one adverse event will be compared between groups using a Fisher exact test. The same approach will be used to compare unexpected reactions (distress, crying, unsettled, vomiting, difficulties feeding, difficulties sleeping, other).

Exploratory analysis

We will:

- Explore explanatory variables at a practitioner level to model between osteopath heterogeneity if present.
- Describe eventual correlation between years of experience and treatment effects (*i.e.* analysis of trends and comparison for cut-off at 3 or less years versus more than 3).
- Investigate eventual association between post-graduate training and treatment outcomes (interaction term).
- Test whether adjunct treatments were similar between both groups to assess unequal treatment bias.

Sensitivity analyses

In a worse-case scenario in an intention to treat (ITT) analysis, we will replace those who are lost to follow-up and missing data for primary outcome with highest observed crying times values in the TTR group and lowest crying time values in the GTR group.

Attrition bias could occur if the number of consultations is unevenly distributed between groups. Therefore, secondary analysis will verify that results are not influenced by uneven distribution of number of consultations. This will be done using random-effects generalised least-square regression adjusting for lack of independence at practitioner level.

Complementary confirmatory analysis

- Separate analysis between 1st and 2nd week (stratified analysis underpowered).
- If baseline imbalance (p -value <0.10) is observed, a secondary analysis with adjustment for these variables will be run to confirm results.
- Per protocol analyses.

All analysis will be intention-to-treat (ITT) except for a secondary per protocol analysis on the primary outcome. All P values will be two sided, and the significance level set at 5%. All statistical analysis are to be done using StataCorp. 2017. Stata Statistical Software: Release 15. College Station, TX: StataCorp LLC. Statistical analysis is managed by [name] who is responsible of preprogramming the entire analysis prior to data collection, of justifying protocol deviation and obtaining approbation from the trial steering committee whilst still blinded from allocation, of running the analysis and delivering the statistical report.

Stopping rule

There are no statistical stopping rule. The trial will be stopped if another high-quality definitive research trial shows that this type of intervention is either highly effective, or is harmful and renders the continuation of this trial inappropriate. The Data Monitoring Committee (DMC) will review the data after 75 infants have been recruited and followed up, to determine progress. The trial will not proceed if more than half the parent participants do not complete their crying diaries, withdraw from the study or if the DMC considers that participants experience too many serious adverse events.

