Number of Participants with Rationale	The data collected on crying time and standard deviations (SD) during the pilot phase (n=13, one diary was completed incorrectly) was consistent with observations made by Wolke et al. (2017). We estimated the average daily crying time over the two-week follow-up period to be 120 minutes with a SD of 46 minutes. To detect a minimum of 30 minutes additional reduction in crying time between the intervention and control groups, with 90% power and a two-sided 5% significance level, we would need 48 infants in each arm of the trial. If we allow for a 15% drop out rate, we will need to randomise 112 infants or 56 in each arm. Given there are three recruiting sites (UK, Australia, Switzerland), each site is to recruit 40 participants.
Study Intervention	Usual osteopathic care with osteopathic manual therapy treatment involving light touch for 10–20 minutes from one to four times over two weeks. Touch is directed at specific areas of the baby's body as deemed appropriate by the osteopath with the intent of bringing change to tissue function or fluid dynamics. Best practice advice will be drawn from the national UK guidance (NICE 2017, https://cks.nice.org.uk/colic-infantile)
Control Intervention	Usual osteopathic care including advice with non-specific generic light touch attention control on cranium, thorax, abdomen and sacral area in any order without any attempt by the osteopath to move or adjust soft tissues or modify fluid mechanisms. During touch, osteopaths undergo a cognitive task to divert attention from touch and avoid conscient

	interactions. Overall consultation duration is of 30-45 minutes, duration of targeted tension release is of 10-20 minutes, 1-4 times over two weeks.

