4 STUDY POPULATION AND STUDY PROCEDURES

4.1 Inclusion and exclusion criteria, justification of study population

One hundred and twenty infants, 40 from Switzerland, are to be included in a 1:1 ratio between OMT and control group. One parent and their infant are to be enrolled. The parent is the person who has legal authority over the child and takes care of the child most of the time. In case of equally shared parenthood, parents choose one person who will be responsible of reporting crying time and answering questionnaires.

Inclusion criteria for parents

- Legal representative of an infant responding to inclusion criteria.
- Age of 18 years or above.
- Mastery of French, German or English to understand the information and consent form, and answer questionnaires.
- Able to give informed consent as documented by signature.

Inclusion criteria for infants

- Infants aged from 1 to 10 weeks (8 to 70 days). This time-frame is important as unsettled crying usually resolves spontaneously after 12 weeks of age and the treatment period is to last two weeks.
- Infants are healthy and thriving.
- Excessively crying, distressed or unsettled for more than 3 hours per day, more than 3 days per week for 1 week or more. This definition is adapted from the Rome IV criteria used in the postnatal clinical classification of infants with difficulties settling, distress and excessive crying

Exclusion criteria for infants

- Active co-morbidities that require medical attention or treatment. This is to limit serious confounders and ensure that the infants recruited are healthy and thriving and that osteopathic care is not inappropriate.

- Priorly or under treatment with an osteopath for similar reasons.
- Already in a clinical trial.

Vulnerable population

This study includes vulnerable participants. Including young infants is justified by the fact unsettled crying is specific to this age group and older children or adults are not affected. Consent from infants is impossible to obtain given their young age (≤ 70 days). Both in the UK and in Switzerland, parents often seek complementary/integrated care during the period after they are discharged by their gynaecologist and before their child is managed by a paediatrician. Apparently, there is a high demand for support during this period. Parents are already seeking care for which no evidence of benefit exists.

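### At the stated SD of 46 minutes, 48 evaluable infants per arm and 112 randomised fall slightly short of 90% power; the planned 120 does not, so the sample size text needs a minor correction

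*Protocol*

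**What the plan says.** Section 5.1 takes the "average daily crying time over the two-week follow-up period to be 120 minutes with a SD of 46 minutes". It sets the aim as "To detect a minimum of 30 minutes additional reduction in crying time between the intervention and control groups". Power is set at 90% and the test is two-sided at 5%. From these inputs it concludes: "we would need 48 infants in each arm of the trial. If we allow for a 15% drop-out rate, we would need to randomise 112", that is, 56 per arm. The synopsis repeats the derivation ("we would need 48 infants in each arm of the trial. If we allow for a 15% drop out rate, we will need to randomise", followed by the same total of 112).

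Both paragraphs then move to a different total. Section 5.1 continues: "Each country is expected to enrol 40 participants or four patients from 10 secondary sites". The synopsis likewise assigns 40 to each of the UK, Australia and Switzerland. Three times 40 is 120, and section 4.1 states that total outright: "One hundred and twenty infants, 40 from Switzerland, are to be included in a 1:1 ratio between OMT and control group".

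Section 5.2 adds that participants who drop out or cannot be followed will be replaced by new subjects. No sentence says how 112, 120 and the replacement rule relate to one another.

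**The concern.** Two things stand out. The 48 per arm looks too low for its own inputs, and 56 per arm does not leave 48 after a 15% loss. Both slips run in the same direction. In addition, the sample size text presents 112 as the number needed and never says what the further 8 infants are for, so they can be read as spare.

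At stake is the accuracy of the power statement. Anyone who relies on 112 as the number that secures 90% power would be working from a figure that, with the planned loss, does not quite secure it.

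**Working it through.** **Inputs.** Difference 30 minutes, SD 46 minutes, power 90%, two-sided 5% and drop-out 15% are from section 5.1. The 1:1 allocation is from section 4.3. Infants are treated as independent.

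**Evaluable infants per arm, normal approximation.**
n = 2 × (1.960 + 1.2816)² × SD² / difference² = 2 × 10.508 × 2116 / 900 = 49.4, so 50 per arm.

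**Evaluable infants per arm, t-test.** The noncentral t calculation gives 50.4, so 51 per arm. Power is 89.8% at 50 and 90.3% at 51.

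The stated 48 is therefore 2 below the first answer and 3 below the second.

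**Power at 48 per arm.** The standard error is 46 × √(2/48) = 9.39 minutes, and 30/9.39 − 1.960 = 1.235. This gives 89.2% by the normal approximation; the t-test gives 88.5%.

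**Drop-out step.** The stated 56 per arm can be reached in two ways: 48/0.85 = 56.5 rounded down, or 48 × 1.15 = 55.2 rounded up. Neither preserves the 48, because 56 × 0.85 = 47.6. Rounding 56.5 up gives 57 per arm, or 114 in total.

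**Power by number randomised, 15% lost and not replaced.**

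| Randomised | Evaluable per arm | Normal | t-test |
|---|---|---|---|
| 112 | 47.6 | 88.9% | 88.3% |
| 114 | 48.45 | 89.4% | 88.8% |
| 118 | 50.15 | 90.4% | 89.9% |
| 120 | 51.0 | 90.9% | 90.3% |

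On the t-test, the difference detectable with 90% power is 30.9 minutes at 47.6 per arm and 29.8 minutes at 51 per arm.

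**Working back from each requirement.** 50/0.85 = 58.8, so 59 per arm and 118 in total. 51/0.85 = 60 per arm and 120 in total.

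**If every drop-out were replaced.** 112 would mean 56 evaluable per arm, with power 93.2% (normal) or 92.8% (t-test). 120 would mean 60 per arm, with 94.7% or 94.3%. What the target counts therefore moves the power by more than the rounding does.

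**The case against.** The case for leaving the text alone is that the discrepancy is at rounding level. At 48 per arm power is within about 1.5 points of 90% by either method. The SD comes from a pilot with 13 usable diaries. If it is a simple estimate with 12 degrees of freedom from normal data, its 95% interval runs from 46 × √(12/23.34) = 33 to 46 × √(12/4.404) = 76 minutes, which dwarfs a gap of two or three infants per arm. Inflating by 1.15 gives exactly 112. And 120 is reachable from the sample size paragraphs themselves, which go straight from 112 to 40 per country, so 112 reads naturally as a minimum rounded up to three equal quotas.

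Most of this stands, and it fixes the size of the point. It does not make the printed figures follow from the printed inputs. Both standard methods put 48 below 90%, and 56 per arm leaves fewer than 48 whichever inflation convention produced it.

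A reader might go further than the documents allow in four ways:

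- That only 120 gives 90% power. This holds for equal arms under the t-test. By the normal approximation, which is closer to the Wald test planned for the primary analysis, 118 is enough.
- That recruitment could close at 112 by plan. No section makes 112 a closing point. Section 5.1 states that there is no statistical stopping rule, and its only numerical review point is 75 infants.
- That 47.6 per arm is what 112 would certainly leave. Section 5.2 provides for replacement, so the figure holds only if losses are not replaced.
- That an SD of 45 was used. It would give 47.3, hence 48, by the normal formula, but nothing in the protocol shows that it was.

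**Conclusion.** The stated 48 evaluable per arm and 112 randomised are slightly too low for the stated 90% power. The requirement is 50 or 51 evaluable per arm, depending on the method, and the inflation step loses a further fraction of an infant per arm. With 15% unreplaced loss, 112 gives about 88 to 89% power, a shortfall of 1 to 2 points.

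It would be wrong to infer that the trial is underpowered. The planned enrolment of 120 leaves 51 per arm and about 90 to 91% power. This is a minor correction of stated figures and of an unexplained pair of totals, not a fault in the design. The conclusion rests on the protocol's own difference, SD and drop-out rate, on equal arms, and on a simple two-group comparison of means.

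**What to change.** In the synopsis and in section 5.1:

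- Restate the requirement as 50 to 51 evaluable infants per arm and name the method. For example, the t-test gives 51 per arm, and 51/0.85 = 60 randomised per arm, 120 in total.
- Name 120 as the single recruitment target, in line with section 4.1 and 40 per country.
- State how the 15% allowance fits with the replacement of drop-outs in section 5.2: whether 120 counts all infants randomised, or whether replacements come on top of it.
- If 112 is kept, label it a calculated minimum and give its power as about 88 to 89% after 15% unreplaced loss.

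The cost is a wording change in two places. No infants are needed beyond the 120 already planned.

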Statistical Considerations	Differences in outcomes, eg. mean crying time, will be compared between groups using a multilevel mixed-effects generalised linear model (GLM) adjusting for lack of independence at site and at practitioner level. Mean crying time will be entered as the dependent variable and group allocation as the explanatory variable. Results will be reported as between-group differences in average crying time in hours with 95% confidence intervals. P-values will provide the probability of this difference being null using Wald Chi2 test. If clustering effects cannot be identified (p-value>0.05), further analysis (i.e. sensitivity analysis, adjusted analysis, etc.) will use simple logistic regression without accounting for lack of independence. All analysis will be intention-to-treat (ITT) except for a secondary per protocol analysis on the primary outcome. All P values will be two sided, and the significance level set at 5%. All statistical analysis are to be done using StataCorp. 2017. Stata Statistical Software: Release 15. College Station, TX: StataCorp LLC.
Inclusion- / Exclusion Criteria	Excessive crying from infants can cause distress and lack of sleep in parents. Parents therefore seek solutions to reduce their infant's crying time. Such treatments are already common in UK, Australia and Switzerland without clear indication on its true benefit. Unsettled crying usually does not affect infants over 6 months of age. To evaluate the true benefit of osteopathic manual care, it is therefore necessary to involve infants. The trial will include infants (from age 1 week to under 10 weeks) who are healthy and thriving but are excessively crying, distressed or unsettled and or fussing and difficult to console. Excessive crying is defined as crying for more than 3 hours per day, more than 3 days per week for more than 1 week and is based on the Rome IV criteria used in the postnatal clinical classification of infants with difficulties settling, distress and excessive crying. Infants will be excluded if they: 
 • have active co-morbidities that require medical attention or treatment prior to enrolment, • have already received osteopathic treatment, • have no tension in their bodies as palpated by the osteopath, • have neither parent who can understand and read German, French or English.

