Study procedures	
Recruitment: Thirty UK, Australian and Swiss osteopaths will recruit participants in their own clinics. In Switzerland, at least 10 osteopaths are to be recruited. When a parent with a crying, distressed and unsettled baby calls the clinic to book an appointment, the osteopath, or their receptionist, will determine whether the baby fits the inclusion criteria, inform the parent about the study, and send them an invitation letter, the participant information leaflet and a consent form. All those interested in the study will be asked to record the number of minutes their baby cries in the 24 hours preceding their booked appointment. When the interested parents turn up for their baby's consultation they will be given the chance to ask questions about the study and asked if they want to participate. After providing their informed consent, parents will have their baby examined and screened to check overall health. If the baby is healthy, they will formally be enrolled in the trial and receive a unique identification study number (ID) and the parent will be asked to complete the baseline questionnaire online on a dedicated GCP and Data protection act compatible eCRF based in the Netherlands (CastorEDC) using the baby's unique ID.
 
Randomisation, allocation and blinding: Block randomization is used to generate the randomization list to allocate patients to either the study or control interventions. Infants will be allocated to their group after baseline values are collected using the online data entry and patient management system (CastorEDC). There will be a standardised communication protocol between the osteopath and the parent during both the study and control intervention. The parents will therefore be 'blinded'. The parents will NOT be informed which treatment arm their infant has been assigned to, but they will be aware that the infant is receiving either the targeted or generic tension release. The parent will be present throughout the treatment and free to observe the delivery of the intervention. For the analysis the statistician will be blinded to the coding of each group.
 
Data collection: Prior to the first treatment parents will complete a baseline questionnaire, a parenting confidence questionnaire, and a 24 hour crying diary. Parents will be required to complete an online crying diary every day for 14 days and record the dates and time of all treatments given. All participating parents will receive a questionnaire for follow-up information at 14 days, containing the parenting confidence questionnaire, a global impression of improvement question and a parent satisfaction questionnaire (please see section on data collection and outcomes). 14 days after randomisation (the first consultation), after completion of all questionnaires, parent can be informed in which treatment arm their infant was allocated to.

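### If the clustering test is non-significant, follow-up analyses of continuous crying time go to logistic regression, which cannot give the planned difference in hours

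*Protocol*

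**What the plan says.** Protocol section 5.1 (Primary outcome analysis) sets up a multilevel mixed-effects model with site and practitioner levels. The outcome is continuous: "Mean crying time will be entered as the dependent variable and group allocation as the explanatory variable". The effect measure is fixed as well: "Results will be reported as between-group differences in average crying time in hours with 95% confidence intervals".

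The same paragraph adds a test, "Likelihood ratio test will be used to test for clustering effects", and a rule that depends on it. If p>0.05, later analyses "will use simple logistic regression without accounting for lack of independence". The synopsis (Statistical Considerations) gives the same trigger, "If clustering effects cannot be identified (p-value>0.05), further analysis", and the same model: "further analysis (i.e. sensitivity analysis, adjusted analysis, etc.) will use simple logistic regression without accounting for lack of independence".

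The analyses in reach of this rule are those that section 5.1 lists without a model of their own. They include the worst-case replacement of missing primary outcomes and the analysis adjusted for baseline imbalance. One listed analysis does name its own model: the check on number of consultations uses random-effects generalised least squares with a practitioner level.

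**The concern.** A logistic model takes a 0/1 outcome and returns an odds ratio. Mean crying time is neither binary nor a proportion, and the protocol defines no responder threshold for it. The rule therefore names a model that cannot be fitted to the stated outcome and cannot return the stated effect measure.

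The analyses at stake are the robustness checks on the primary result. Section 5.2 says that missing data cannot be assumed to be missing at random, yet takes complete cases as the main analysis. The worst-case analysis is the check on that choice. The adjusted analysis is there to confirm the result if baseline values are unbalanced. Neither can be set against the 30-minute target difference if it is on the odds-ratio scale. If someone picked a cut-point to make the model run, that choice would not be prespecified, and the check would lose power.

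**Working it through.** **1. Can the rule be run as written?** Outcome: mean minutes or hours per day. Effect measure: difference in hours with a 95% CI. Fallback model: logistic. Fitting a logit model to simulated minutes (mean 120, SD 46) stops with an error, because the outcome must lie between 0 and 1. The sentence cannot be read as meant for the Likert outcomes: it stands under the primary outcome, and section 5.1 gives those outcomes a proportional odds model of their own.

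**2. The plan's own sample size.** Inputs from section 5.1: difference 30 min, SD 46 min, two-sided 5%, 90% power.
- n per arm = 2 × [46 × (1.960 + 1.282) / 30]² = 49.4, so 50. The protocol states 48, within 2 infants.
- Power at 48 per arm: 30 / (46 × √(2/48)) = 3.195, and Φ(3.195 − 1.960) = 0.892, or 89%. This is the power of a linear comparison.

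**3. Power if crying time were dichotomised to make the fallback run.** Assumptions: normal outcomes, means 120 and 90 min, SD 46, 48 per arm. The cut-offs c are assumed, because the protocol gives none. Proportions below the cut-off are p₁ = Φ((c − 120)/46) and p₂ = Φ((c − 90)/46). Power = Φ((|p₁ − p₂| − 1.960 × SE₀)/SE₁), with SE₀ the pooled and SE₁ the unpooled standard error.

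| Cut-off (min) | p₁ | p₂ | Power, 48 per arm | n per arm for 90% |
|---|---|---|---|---|
| 60 | 0.096 | 0.257 | 54.5% | 116 |
| 90 | 0.257 | 0.500 | 69.5% | 82 |
| 105 | 0.372 | 0.628 | 71.3% | 79 |
| 120 | 0.500 | 0.743 | 69.5% | 82 |
| 180 | 0.904 | 0.975 | 30.5% | 237 |

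For c = 120: difference 0.243, SE₀ 0.0990, SE₁ 0.0959, so Φ((0.243 − 0.194)/0.0959) ≈ 0.695.

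**4. How often is the fallback taken?** Cluster structure: "Thirty UK, Australian and Swiss osteopaths will recruit participants in their own clinics" (synopsis) and "Each country is expected to enrol 40 participants or four patients from 10 secondary sites" (section 5.1). That gives k = 30 practitioners with m = 4 infants each, or m = 120 × 0.85 / 30 = 3.4 after 15% drop-out. The protocol gives no ICC, so a range is assumed.

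With no clustering, a 5% test is non-significant about 95% of the time. Otherwise, take a one-way F test on practitioners as an approximation to the likelihood ratio test. With λ = 1 + m × ICC/(1 − ICC), power = P(F > F₀.₉₅/λ) on k − 1 and k(m − 1) degrees of freedom.

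| ICC (assumed) | Power, m = 3.4 | Power, m = 4 | Fallback taken |
|---|---|---|---|
| 0.05 | 13.7% | 16.4% | 84-86% |
| 0.10 | 28.2% | 35.3% | 65-72% |
| 0.20 | 64.3% | 75.2% | 25-36% |

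A simulated likelihood ratio test (30 × 4, no site variance, several reference distributions) had lower power: 3-13%, 10-30% and 43-71% at the same ICCs. On those figures the fallback would be taken somewhat more often.

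**The case against.** **It may be a slip for "linear".** Probably so, and it would show itself as soon as the model was programmed. Section 5.1 also has the whole analysis preprogrammed before data collection, with deviations justified and approved while blinded, so silent harm is unlikely. This stands as a limit on the harm. It does not make the text right: the sentence appears twice, and departing from it without an amendment is itself a deviation.

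**The reach is limited.** This stands. The switch is conditional, the primary estimate with its interval and p-value is never switched, and the consultation-number analysis keeps its own model. A reader might infer that every follow-up analysis is lost or that the primary result is in doubt. The protocol supports neither.

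**The power of the clustering test is not the cause.** This stands too. A reader might infer that the test has almost no power and that the checks fail for that reason. With a linear fallback, a non-significant test would still lead to a usable check on the right scale. Infants are randomised individually, so dropping the practitioner term mainly affects precision. Low power only makes the wrong model the likelier route, and it is low only if the ICC is not large.

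**The trigger percentages are illustrative.** The F test ignores the site level, and the cluster structure may differ. Section 4.3 reports that only 25% of trained pilot osteopaths went on to recruit, which led to dedicated trial clinics. With 12 practitioners and 10 infants each (an assumption), the same F test has 28%, 55% and 87% power at ICCs of 0.05, 0.10 and 0.20.

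**Conclusion.** The rule is wrong as written. It assigns a model for binary outcomes to a continuous outcome whose effect is to be reported in hours, and it supplies no cut-point. This follows from the text alone and needs no assumption.

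Its size depends on two things that the protocol does not give. If crying time were dichotomised, the loss depends on the cut-off and on normality with the planning means and SD. The chance of reaching the fallback depends on the ICC and on how infants are spread over practitioners. Over the ranges examined, the power loss is material at every cut-off, and with 30 practitioners the fallback is the more likely route unless the ICC is large (near 0.20). The fault lies in the model named for the follow-up analyses, and nothing here shows the primary model to be wrong.

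**What to change.** In section 5.1 and in the synopsis, replace the simple logistic regression with linear regression, and state that every analysis of crying time reports a between-group difference in hours with a 95% CI.

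Preferably, drop the conditional switch. For example: *Sensitivity, adjusted and per-protocol analyses of crying time use the same mixed model as the primary analysis, whatever the result of the clustering test.* The consultation-number analysis can keep its stated model.

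The cost is one sentence in each of two places and no new data. Because the analysis is pooled across countries, the same wording should be checked in the lead UK protocol and any statistical analysis plan. If the change is judged substantial, it needs steering committee and ethics approval under sections 6.4 and 9. It should be made before unblinding.
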